7.3. Unscheduled Visits

If, during the investigation, a subject requires an unscheduled visit to the clinical site, the following information will be collected, as appropriate:

- Chief complaint prompting the visit. If the reason is an adverse event, the applicable eCRF for the adverse event must be completed and subject record completed as appropriate.
- Date and time of the visit and all procedures completed at the unscheduled visit.
- Review of adverse event and concomitant medications.
- Documentation of any test article dispensed or collected from the subject, if applicable.
- Slit lamp findings (using the Slit Lamp Classification Scale).

If the Investigator withdraws a subject from the study, the final study visit case report forms must be completed indicating the reason(s) why the subject was withdrawn. The subject record

Clinical Study Protocol
Johnson & Johnson Vision Care, Inc.

must be completed documenting the date and primary reason for withdrawal and the study CRA notified.

Any ocular and non-ocular Adverse Events that are ongoing at the time of the study visit will be followed by the Investigator, within licensure, until they have resolved, returned to pre-treatment status, stabilized, or been satisfactorily explained. If further treatment i.e., beyond licensure is required, the subject will be referred to the appropriate health care provider.

The following information will be collected during an unscheduled visit.

Unscheduled Visit		
Step	Procedure	Details
U.1	Reason for unscheduled visit	Indicate if the only reason for the visit is that the subject requires additional test articles. If the reason is other than resupply of previously dispensed lenses, specify the reason for the visit.
U.2	Chief Complaints (if applicable)	Record the subject's chief complaints for reasons for the unscheduled visit.
U.3	Adverse Events and Concomitant Medications Review (if applicable)	Review any changes to the subject's medical history or concomitant medications from the previous study visit. Record any changes, and any adverse events.
U.4	Entrance VA (if applicable)	Record the entrance distance visual acuity (OD, OS, OU) to the nearest letter.
U.5	Subjective Sphero-cylindrical Refraction (if applicable)	Perform bare-eye subjective sphero-cylindrical refraction with a phoropter (adopt the maximum plus to maximum visual acuity (MPMVA) approach and record the best corrected distance visual acuity to the nearest letter (OD, OS, OU).

Clinical Study Protocol
Johnson & Johnson Vision Care, Inc.

Unscheduled Visit		
Step	Procedure	Details
U.6	Slit Lamp Biomicroscopy (if applicable)	
FDA Slit Lamp Classification Scale will be used to grade the findings. If the clearance of the fluorescein needs to be expedited, preservative-free rewetting drops may be instilled.
 
If the subject has a Grade 3 slit lamp finding, it will be recorded as an Adverse Event and the subject will be monitored as per the guidelines given in section 13.
 
In addition, Limbal and Bulbar Conjunctival Hyperemia findings and detailed Corneal Staining Assessment will be recorded using a more detailed scale for internal purposes only. Conjunctival hyperemia should be assessed using the 0.5 increment grading scale.

U.7	Dispensing (if applicable)	If the subject requires additional lenses to complete the wear period and is eligible to do so, provide additional lenses per the dispensing instructions given in the detailed study procedures.
U.8	Exit Visual Acuity (if applicable)	Record the subject's exit distance visual acuity (OD, OS and OU) to the nearest letter.

NOTE: If the only reason for the unscheduled visit is that the subject requires additional test articles, only the dispensing information needs to be recorded.

7.4. Laboratory Procedures

Not Applicable.

8. SUBJECTS COMPLETION/WITHDRAWAL

8.1. Completion Criteria

Subjects are considered to have completed the study if they:

- provided informed consent.
- they are eligible.
- have not withdrawn/discontinued from the study for any reason described in section 8.2.
- completed all visits through the final visit (Visit 3).

Clinical Study Protocol

Johnson & Johnson Vision Care, Inc.

- If all visits were completed but an additional visit is considered necessary for subject care, follow the requirements for unscheduled visits in section 7.3.

8.2. Withdrawal/Discontinuation from the Study

A subject will be withdrawn from the study for any of the following reasons:

- Subject withdrawal of consent.
- Subject not compliant to protocol (e.g., out of window more than 2 days).
- Subject lost to follow-up.
- Subject no longer meets eligibility criteria (e.g. the subject becomes pregnant).
- Subject develops significant or serious adverse events necessitating discontinuation of study lens wear.
- Subjects who have experienced a Corneal Infiltrative Event (CIE).
- Investigator's clinical judgment regarding the subject safety reasons (that it is in the best interest of the subject to stop treatment).
- Subject missed any study visits.
- Subject not compliant with study lens wear schedule.
- Subject not successfully dispensed due to lack of efficacy and safety including poor vision, poor comfort or unacceptable fit.

For discontinued subjects, the Investigator will:

- Complete the current visit (scheduled or unscheduled).
- Complete the Final Evaluation, indicating the reason that the subject was discontinued from the study.
- Record the spherocylindrical refraction with best corrected distance visual acuity.
- Collect used test article(s) (worn or brought to the visit) from the subject and discard them, unless otherwise stated in section 7.2.
- Collect all unused test article(s) from the subject.
- Make arrangements for subject care, if needed, due to their study participation

Additional subjects will be enrolled if a subject discontinues from the study prematurely.

In cases where a subject is lost to follow-up, every possible effort must be made to contact the subject and determine the reason for discontinuation/withdrawal. The measures taken to follow up must be documented including two written attempts and a certified letter (or equivalent) as the final attempt.

9. PRE-STUDY AND CONCOMITANT INTERVENTION/MEDICATION

Concomitant medications will be documented during screening and updated during the study.

- Disallowed medications for this study include: any ocular medication.
- Concomitant therapies that are disallowed include: See section 9.1.

Clinical Study Protocol

Johnson & Johnson Vision Care, Inc.

9.1. Systemic Medications

Certain systemic medications are known to have a higher likelihood to interfere with contact lens wear, chiefly by disrupting the tear film.

A summary of disallowed systemic medications is shown in Table 4. Subjects with a history of taking these medications will be allowed to enroll only if:

- The medications have been taken on a continual, routine basis for at least 6 months, and
- The subject has demonstrated successful contact lens wear during this time.

Or:

- The subject was taking the medication on a temporary basis and ceased taking that medication at least 2 weeks prior to signing the informed consent (this is considered sufficient time for the medication to have left the body prior to enrollment).

Subjects with a history of taking medications listed in Table 4 on a long-term, routine basis for less than 6 months will not be allowed to participate in the study.

Table 4: Disallowed systemic medications

Class of Drug	Common Indication(s)	Common Examples
Estrogens (not including contraceptive medication)	Menopause, osteoporosis, vaginitis	Vagifem, Estrace, Climara, Vivelle-Dot, Premarin, Minivelle, etc.
Anticholinergics	Irritable bowel syndrome, Parkinson's disease, peptic ulcer, cystitis, nasal congestion, cold symptoms, overactive bladder, COPD	Bentyl, Spiriva, Atrovent, Hyosyne, Levsin, Symax Fastab, Symax SL, Homax SL, Cogentin, Transderm Scop, etc.
Beta-blockers	Hypertension, angina, heart attack, migraine, atrial fibrillation, adrenal cancer, essential tumor, glaucoma	Toprol XL, Lopressor, Tenormin, Propranolol, Timoptic, Trandate, Inderal LA, etc.
Psychotropics	Antipsychotic (schizophrenia, mania), antidepression, antiobsessive, antianxiety, mood stabilizer, stimulants (ADHD)	Zoloft, Celexa, Prozac, Lexapro, Effexor, Cymbalta, Ativan, Xanax, Desyrel, Wellbutrin, etc.
Vitamin A analogs	Cystic acne	Isotretinoin

Examples of disallowed systemic antihistamines are given in Table 5. Subjects with a history of taking systemic antihistamines will be allowed to enroll only if:

Clinical Study Protocol

Johnson & Johnson Vision Care, Inc.

- They have taken antihistamines continuously for at least 2 weeks, and
- They have demonstrated successful wear while taking the medication

Or:

- They stopped taking the medication for at least 2 weeks prior to enrollment.

Table 5: Disallowed systemic antihistamines

Class of Drug	Common Indication(s)	Common Examples
Antihistamines	Allergic rhinitis, sedation, hives, allergic conjunctivitis, skin allergy, itching, motion sickness	Hydroxyzine, Promethagan, Phenadoz, Vistaril, Claritin, Zyrtec, Astepro, Astelin, Optivar, Allegra, Benedryl, etc.

10. DEVIATIONS FROM THE PROTOCOL

Investigator will notify study sponsor upon identification of a protocol deviation. Protocol deviations must be reported to the sponsor within 24 hours after discovery of the protocol deviation. The Investigator will report deviations per IRB/IEC requirements. All deviations will be tracked, and corrective actions implemented as appropriate.

If it becomes necessary for the Investigator to implement a deviation in order to eliminate an immediate hazard to the trial subject, the Investigator may implement the deviation immediately without notification to the sponsor. Within 24 hours after the implemented deviation, the Investigator must notify and provide the rationale to the Sponsor and as required, to the IEC/IRB.

If the deviation potentially impacts the safety of patient or changes the technical integrity of the study, then it must be reported to IEC/IRB. This is a "Major Deviation". Deviations that contradict the information contained in the Informed Consent/Assent forms will be considered Major Deviations.

Minor deviations have no substantive effect on patient safety or technical integrity of the study. They are often logistical in nature.

Protocol waivers are prohibited.

Table 6 lists examples of deviations that will constitute major and minor protocol deviations for this study.

Clinical Study Protocol
Johnson & Johnson Vision Care, Inc.

Table 6: Examples of major and minor protocol deviations

Deviation category	Major deviation	Minor deviation
Out-of-window visit	Visit attended more than 2 days out of visit window defined in study procedures.	Visit attended 2 or fewer days out of visit window defined in study procedures.
Unanswered PRO questions	For questionnaires where data is related to a primary or secondary endpoint, more than 2 PRO questions are unanswered (i.e., left blank).	For questionnaires where data is related to a primary or secondary endpoint, 2 or fewer PRO questions are unanswered (i.e., left blank). For questionnaires where data is not related to a primary or secondary endpoint, any PRO questions are unanswered (i.e., left blank).
Insufficient wear of study lenses	Subject does not wear study lenses for at least 6 hours on at least 5 days of a study lens wear period.	Subject does not wear study lenses attending a follow-up visit.

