2.16	Continuance	
For the subject to continue in the study, they must meet all three of the following criteria:
 
 • Visual acuity is 20/30 or better OD and OS. • The lens fit is acceptable OD and OS. • Investigator approval. 
If the Investigator does not approve the dispensing of the first study lens, then the study is terminated for that subject.

Clinical Study Protocol
Johnson & Johnson Vision Care, Inc.

Visit 2: Treatment 1 Follow-Up 1		
Step	Procedure	Details
2.17	Dispense	
The lenses will be dispensed for a 5-9 day wearing period. During this time, they are required to wear the lenses at least 5 days and at least 6 hours per day that they are worn.
 
 • Dispense enough lenses to last the subject to their scheduled follow-up visit. Do not dispense extras* • The lenses will be worn as daily wear/daily disposable only • Rewetting drops are permitted if needed • Subjects will be scheduled for their 1-week follow-up visit • Subjects should be instructed to wear the study lenses to the follow-up visit and bring their habitual correction with them. 
* Note: In the event a lens is lost or damaged, the subject will return to the clinical site for replacement. As much as reasonably possible, a damaged lens and packaging should be returned to the clinical site (wet, if possible) and then returned to the Sponsor. If lens damage is present, complete the Product Quality Complaint Form. The lens will be stored in labeled vial with saline, and clearly differentiated from the other worn lenses that will be shipped back to the Sponsor.

Clinical Study Protocol
Johnson & Johnson Vision Care, Inc.

VISIT 3

The subjects must present to Visit 3 wearing the study lenses.

Visit 3: Treatment 1 Follow-Up 2		
Step	Procedure	Details
3.1	Adverse Events and Concomitant Medications Review	Review any changes to the subject's medical history or concomitant medications from the previous study visit. Record any changes, and any adverse events.
3.2	Wearing Time	Record the average wearing time and comfortable wearing time.
3.3	Compliance	Confirm compliance with the prescribed wear schedule.
3.4	Lens Collection	Collect any unworn study lenses from the subject.
3.5	Subject Reported Ocular Symptoms	Subjects will respond to a verbal open-ended symptoms questionnaire.
3.6	Follow-Up Questionnaire	The subject will complete the Follow-Up Questionnaire directly.

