3.7	Visual Acuity	Record the distance Snellen visual acuity with the contact lenses (OD, OS and OU) to the nearest letter. Subjects must read the smallest line until at least 50% of the letters are read incorrectly.

Clinical Study Protocol
Johnson & Johnson Vision Care, Inc.

Visit 3: Treatment 1 Follow-Up 2																																	
Step	Procedure	Details																															
3.8	Distance ETDRS LogMAR Visual Acuity	
Measure monocular distance high luminance low contrast (HLLC), and low luminance high contrast (LLHC) visual acuity using ETDRS charts at 4 meters. Chart luminance will be reduced with a filter placed in front of the light box.
 
Measure each eye once using the charts shown in the tables below:
 
 
 Condition	HLLC	
 
 Room illumination	> 400 lux	
 
 Chart luminance	120 - 200 cd/m²	
 
 Eye	OD	OS	
 
 Charts	LC-1	LC-2	
 
 
 
 Condition	LLHC	
 
 Room illumination	\leq 2.5 lux	
 
 Chart luminance	1.5 - 5.0 cd/m²	
 
 Eye	OD	OS	
 
 Charts	HC-1	HC-2	
 
 
Recorded letter-by-letter results into EDC.
	Condition	HLLC		Room illumination	> 400 lux		Chart luminance	120 - 200 cd/m ²		Eye	OD	OS	Charts	LC-1	LC-2	Condition	LLHC		Room illumination	\leq 2.5 lux		Chart luminance	1.5 - 5.0 cd/m ²		Eye	OD	OS	Charts	HC-1	HC-2	
Condition	HLLC																																
Room illumination	> 400 lux																																
Chart luminance	120 - 200 cd/m ²																																
Eye	OD	OS																															
Charts	LC-1	LC-2																															
Condition	LLHC																																
Room illumination	\leq 2.5 lux																																
Chart luminance	1.5 - 5.0 cd/m ²																																
Eye	OD	OS																															
Charts	HC-1	HC-2																															

Clinical Study Protocol
Johnson & Johnson Vision Care, Inc.

Visit 3: Treatment 1 Follow-Up 2		
Step	Procedure	Details

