14.3. Analysis Populations

Safety Population:

All subjects who are administered any test article excluding subjects who drop out prior to administering any test article. At least one observation should be recorded.

Per-Protocol Population:

All subjects who successfully complete all visits and do not substantially deviate from the protocol as determined by the trial cohort review committee prior to database hard lock. Justification for the exclusion of subjects with protocol deviations from the per-protocol population set will be documented in a memo to file.

Intent-to-Treat (ITT) Population:

All randomized subjects regardless of actual treatment and subsequent withdrawal from the study or deviation from the protocol. At least one observation should be recorded.

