14.5. Primary Analysis

The co-primary endpoints for this study are the logMAR VA test at a 4-meter distance under either HLLC or LLHC and the average daily wear time at 2-week follow-up evaluated after 14 ± 4 days of lens wear. The primary analysis will be conducted on per-protocol populations.

Visual Performance

Monocular distance visual performance in logMAR scale at follow-up visits will be analyzed using a mixed model of repeated measurement (MMRM) for HLLC and LLHC respectively to compare between Test and Control lenses at 2-week follow-up. The model will include baseline logMAR, lens type, visit, and the interaction of lens type and visit as the fixed effect, and investigational site and patient as random effects. Baseline demographics such as age and gender have historically limited influence on objective visual performance; thus, in accordance with the principle of parsimony, will not be included in the model. The covariance of residual errors between two follow-up visits across periods for the same eye and subject across wearing periods will be modeled using an unstructured (UN) covariance structure.

The null and alternative hypotheses for non-inferiority of Test lens relative to Control are as follows:

$$H_0: \Delta > 0.05$$
$$H_A: \Delta \leq 0.05$$

Clinical Study Protocol

Johnson & Johnson Vision Care, Inc.

where Δ is the mean difference in logMAR between Test lens and Control lens (Test minus Control) at 2-week follow-up. Non-inferiority will be declared if the upper bound of the confidence interval of the mean difference between Test and Control is less than 0.05.

Average Daily Wearing Time

Average daily wear time will be analyzed using a similar MMRM model with fixed and random effects described in the primary analysis. Age and gender will also be included as fixed effects.

The null and alternative hypotheses for non-inferiority of Test lens relative to Control are as follows:

$$H_0: \Delta < -1$$
$$H_A: \Delta \geq -1$$

where Δ is the mean difference in average daily wearing time between Test lens and Control lens (Test minus Control) at 2-week follow-up. Non-inferiority will be declared if the lower bound of the confidence interval of the mean difference between Test and Control is greater than -1.

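### Arriving at a follow-up visit without the study lenses is classed as a minor deviation, and no visible rule keeps logMAR acuity measured off the assigned lens out of the primary analysis

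*Combined protocol and SAP*

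**What the plan says.** **Endpoint.** Section 2.2 defines visual performance as monocular, contact lens-corrected logMAR acuity at the 2-week visit. Section 14.5 compares Test with Control lenses on it, with a margin of 0.05, and states: "The primary analysis will be conducted on per-protocol populations".

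**Visit procedures (Section 7.2).** The Visit 3 text opens with "The subjects must present to Visit 3 wearing the study lenses", and Visit 2 has the matching line. The logMAR step, numbered 2.7 and 3.8, reads "Measure monocular distance high luminance low contrast (HLLC), and low luminance high contrast (LLHC) visual acuity using ETDRS charts at 4 meters" and does not name the lens worn. The only insertion step at a follow-up visit is 2.14, which comes after that visit's logMAR. Visit 3 has none. At step 2.17 subjects are told to wear the study lenses to the next visit and to "bring their habitual correction with them", and sites are told to dispense no spare lenses.

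**Deviation class (Section 10, Table 6).** In the row on insufficient wear, the minor column reads "Subject does not wear study lenses attending a follow-up visit". The text above the table says "Minor deviations have no substantive effect on patient safety or technical integrity of the study".

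**Analysis set (Section 14.3).** The per-protocol set is "All subjects who successfully complete all visits and do not substantially deviate from the protocol as determined by the trial cohort review committee", decided before hard lock with the reasons documented.

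**The concern.** An acuity reading taken without the assigned lens carries no information on either product. Table 6 foresees that some subjects will arrive without the lens, and classes this as harmless to technical integrity at the very visit where a co-primary endpoint is measured. The same table makes more than 2 blank items on a questionnaire tied to a primary or secondary endpoint a major deviation, so the ranking looks inverted for acuity.

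The stake is specific to non-inferiority. Readings that come from neither lens, taken at similar rates in both arms and in a good correction, pull the arm means together. In a superiority trial that is conservative. Here it favours the claim. If the eye is uncorrected, the main harm is different: a few very poor readings inflate the variance and can make a sound lens fail. Section 2.3 requires both co-primary hypotheses to be met for study success, and Section 14.2 says the data will be used to design later trials.

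**Working it through.** **Inputs from the documents.** Margin 0.05 logMAR (Sections 2.3 and 14.5); SD 0.08 to 0.10 (Table 7); 100 completers, about 50 per arm (Section 14.2); type I error 0.05, described in Section 14.2 as two-sided; success if the upper confidence bound is below 0.05 (Section 14.5).

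**Assumptions.** The off-lens share f and the off-lens acuity are not in the documents. The share is taken as equal in both arms. As in Table 7, each subject contributes one value to a two-sample t-test.

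**1. Reproducing Table 7.** At SD 0.10 and true difference 0:

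- SE = 0.10 × √(2/50) = 0.020
- Noncentrality = 0.05/0.020 = 2.5, with 98 degrees of freedom
- Power = 0.799 at one-sided 0.05, which matches the table, and 0.697 at one-sided 0.025

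All six rows of Table 7 reproduce at one-sided 0.05 and none at one-sided 0.025. The model is therefore the plan's own. Because the text says two-sided 0.05, error is shown below at both levels.

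**2. Off-lens in a good correction.** Let off-lens acuity have the control-level mean in both arms. Then:

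- Expected difference = (1 − f) × Δ. For Δ = 0.05 this is 0.049, 0.0475 and 0.045 at f = 2%, 5% and 10%.
- Averaged over the arms, the variance becomes SD² + ½ f(1 − f)Δ². At f = 10% and SD 0.10 this is 0.0100 + 0.0001125, giving SD 0.1006.
- Noncentrality = (0.05 − expected difference)/SE. At f = 10%: 0.005/(0.1006 × 0.2) = 0.249, against 0 with no off-lens readings.

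Probability of declaring non-inferiority when the true deficit equals the margin (noncentral t, 98 df):

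| f | SD 0.10, one-sided 0.025 | SD 0.08, one-sided 0.025 | SD 0.10, one-sided 0.05 | SD 0.08, one-sided 0.05 |
|---|---|---|---|---|
| 0 | 2.5% | 2.5% | 5.0% | 5.0% |
| 2% | 2.8% | 2.9% | 5.5% | 5.7% |
| 5% | 3.3% | 3.6% | 6.4% | 6.8% |
| 10% | 4.3% | 4.9% | 8.1% | 9.1% |

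With 50 per arm, 2% is one subject per arm and 10% is five.

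**3. Off-lens and uncorrected.** Assume a shift of +0.5 logMAR (SD 0.2) or +0.8 logMAR (SD 0.3) in both arms, with on-lens SD 0.10. At f = 2% and no true difference, the variance within an arm is:

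- Shift +0.5: 0.98 × 0.01 + 0.02 × 0.04 + 0.02 × 0.98 × 0.25 = 0.0155, so SD is about 0.12
- Shift +0.8: 0.98 × 0.01 + 0.02 × 0.09 + 0.02 × 0.98 × 0.64 = 0.0241, so SD is about 0.16

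In simulation (40,000 trials per cell, one-sided 0.025), the error at a true deficit of 0.05 stays at about 2.3% to 3.0% for f from 2% to 10%. Power at no true difference falls from about 0.70 to 0.54 (shift +0.5) or 0.42 (shift +0.8) at f = 2%.

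**The case against.** The strongest reply is that the protocol plainly intends study lenses to be on the eye. Subjects must arrive in them, step 3.7 records acuity with the contact lenses in place, and steps 3.9 to 3.13 grade, remove and store those lenses. A reader might infer that step 3.8, followed literally, is done in whatever the subject has on. The documents do not support that, since no step directs testing in another correction. What is missing is a fallback when the lenses are absent.

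Three further inferences are tempting and should be resisted:

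- **That a minor deviation automatically stays in the per-protocol set.** Section 14.3 does not use the major and minor labels. A committee decides who fails the test "do not substantially deviate from the protocol", Table 6 gives only examples, and Section 10 requires deviations to be reported within 24 hours and tracked. The committee can exclude such a subject. It lacks a written rule, and the minor label points it the other way.
- **That Table 3 or step 2.17 permits off-lens testing.** The NA entry in Table 3 concerns minimum wear time before the visit. Bringing habitual correction is naturally read as correction for going home, because the study lenses are kept at step 3.13.
- **That off-lens readings always favour non-inferiority.** The third step of the working shows otherwise for uncorrected eyes.

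It also stands that the Appendix D logMAR procedure is redacted and may name the correction worn, that all hypotheses are called exploratory (Section 2.3), and that the inflation is small at low shares.

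What survives is narrower. The safeguards presuppose lens wear without saying what to do when it fails. Habitual contact lenses would satisfy the words contact lens-corrected. The withdrawal reasons in Section 8.2 name general non-compliance and the wear schedule, but a subject can meet the schedule and still arrive without lenses.

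**Conclusion.** The point holds as a gap in the rules. Table 6 treats as inconsequential an event that invalidates a co-primary reading, and nothing visible says what becomes of that reading in the primary analysis.

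The size is modest and conditional. At assumed shares of 2% to 5% tested in a good correction, one-sided error rises from 2.5% to between 2.8% and 3.6% across the plan's SD range. It reaches 4.3% to 4.9% only if 10% of both arms are tested off-lens. If the eyes are uncorrected, the cost is power rather than false success. Both results assume equal shares in the arms, and the uncorrected case also depends on the assumed acuity shifts. The documents give no frequency, so the practical effect is likely small. The correction is worth making because it is cheap and helps whichever way the error runs.

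**What to change.** 1. **Record the lens.** Add a CRF field at steps 2.7 and 3.8 stating which correction was on each eye.
2. **State the rule in Section 14.5.** LogMAR and other lens-on-eye measures (lens-corrected acuity, fit, wettability) not taken on the assigned study lens are set to missing for that visit. The MMRM keeps the subject's other visit, and wear time and CLUE are retained.
3. **Amend the Table 6 cell** so that it no longer implies no effect on technical integrity for those measures.

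**Cost.** One CRF field, one analysis sentence, one table cell and a few missing logMAR values. These values rely on the missing-at-random assumption in Section 14.9 and count towards its 15% trigger for sensitivity analyses. Making the cell major outright would add IEC/IRB reporting under Section 10 and might lead the committee to drop whole subjects, losing valid wear-time and CLUE data. The measure-level rule is therefore the better vehicle.

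A re-insertion step at the visit is an alternative, but it would rely on a settling time that the protocol gives two ways: 10 minutes in Table 3 and a minimum of 5 minutes in step 1.18. The sponsor would have to reconcile those first.
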